**Statistical Methods:**

In general, all efficacy and safety endpoints will be analyzed using descriptive statistics (n, mean, standard deviation, median, and ranges for continuous variables; frequencies and percentages for categorical variables). Kaplan-Meier methods will be used to summarize time-to-event endpoints (OS, PFS, and DOR). Primary efficacy of ORR will be analyzed using the Bayesian approach defined in the statistical analysis plan (SAP). Other efficacy analyses will be performed on the full analysis set (FAS).

Detailed methodology for the statistical analyses of the data collected in this study will be documented in the SAP, which will be maintained by [REDACTED]. The SAP may modify the plans outlined in the protocol; however, any major modifications of the primary endpoint definition and/or its analysis will also be reflected in a protocol amendment.

Patient responses will be assessed based on RECIST v1.1 and iRECIST. Data listings and summaries may include tumor markers, additional imaging, or other response data. Potential relationships between biomarker and other response data may be evaluated. For Phase 2, primary efficacy of ORR with RECIST v 1.1 will be analyzed using the Bayesian approach defined in the SAP, based on ES. Other efficacy analyses will be performed on the FAS. Progression-free survival ratio will be summarized for both the Phase 1b enrichment cohort and for Phase 2.

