## 12. STATISTICS

### 12.1. Statistical Methods

Detailed methodology for the statistical analyses of the data collected in this study will be documented in the statistical analysis plan (SAP), which will be maintained by [REDACTED]. The SAP may modify the plans outlined in the protocol; however, any major modifications of the primary endpoint definition and/or its analysis will also be reflected in a protocol amendment.

In general, all efficacy and safety endpoints will be analyzed using descriptive statistics (n, mean, standard deviation, median, and ranges for continuous variables; frequencies and percentages for categorical variables).

All deviations related to conduct of the study, patient management, or patient assessment will be identified, evaluated, and closed before database lock and will be described in the final CSR. Protocol deviations are not allowed for inclusion or exclusion criteria.

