#### **12.1.2.4. Efficacy Set**

The Efficacy Set (ES) includes all patients from the FAS who have responded to treatment (CR/PR), assessed as progressed on treatment without regard to length of treatment, or have been on treatment for 6 months or more without regard to tumor response status.

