#### **12.1.5. Data Analyses**

##### **12.1.5.1. Efficacy Analysis**

Kaplan-Meier methods will be used to summarize time-to-event endpoints (OS, PFS, and DOR). Primary efficacy of ORR will be analyzed using the Bayesian approach defined in the SAP; other efficacy analyses will be performed on the FAS.

Patient responses will be assessed based on RECIST v1.1 and iRECIST. Data listings and summaries may include tumor markers, additional imaging, or other response data. Potential relationships between PD and other response data may be evaluated. In Phase 2, primary efficacy of ORR will be analyzed using the Bayesian approach defined in the SAP; other efficacy analyses will be performed on the FAS.

Progression-free survival ratio (PFSr) will be summarized for both the Phase 1b enrichment cohort and for Phase 2.

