Objective disease assessments will be performed according to RECIST (v1.1) and iRECIST, with the first assessment performed at the end of the dose-limiting toxicity (DLT) period (Cycle 3: at 4 weeks for nivolumab arm, at 6 weeks for pembrolizumab arm), and at Weeks 12, 18, and 24 after the first dose of DSP-7888 Dosing Emulsion. After that, objective disease assessments will occur every 12 weeks until disease progression.

1.2.1.2.1. Best Overall Responses, Objective Response Rate and Disease Control Rate, and Duration of Response per RECIST (v1.1)

Objective disease assessments will be performed according to RECIST (v1.1) and iRECIST, with the first assessment performed at the end of the dose-limiting toxicity (DLT) period (Cycle 3: at 4 weeks for nivolumab arm, at 6 weeks for pembrolizumab arm), and at Weeks 12, 18, and 24 after the first dose of DSP-7888 Dosing Emulsion. After that, objective disease assessments will occur every 12 weeks until disease progression.

Best Overall Response (BOR) per RECIST (v1.1) is the best response recorded from first dose until disease progression or start of new anti-cancer therapy. Tumor scan assessment done after PD or after “new anti-cancer” treatment will not be considered in the evaluation of BOR. BOR is derived from the sequence of objective response determined by the following order:

- CR: One objective status of CR documented and confirmed (at least 4 weeks after) before progression or start of new anti-cancer therapy
- PR: One objective status of PR documented and confirmed (at least 4 weeks after) before progression or start of new anti-cancer therapy, but not qualifying as CR
- SD: At least 1 objective status of SD or better documented at least 1 nominal scan interval (6 weeks – 2 days window = 40 days) after first dose date and before progression and the start of new anti-cancer therapy, but not qualifying as CR or PR
- PD: Progression documented within 2 nominal scan intervals (or 12 weeks + 2 days window = 86) after first dose date and not qualifying as CR, PR, or SD
- NE: All other cases will be categorized as NE.

Objective Response Rate (ORR) per RECIST (v1.1) is defined as the proportion of patients who have achieved confirmed complete response (CR) or partial response (PR), evaluated using RECIST (v1.1) by investigator assessment.

The patients will be considered as non-responders until proven otherwise. Thus, the patients who:

- Do not have CR or PR while on study; or

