- Do not have a baseline or post-baseline tumor evaluation; or
- Do not have an adequate baseline tumor evaluation; or
- Receive new anti-cancer treatment other than the study medication prior to reaching a CR or PR; or
- Die, progress, or drop out for any reason prior to reaching a CR or PR

are considered non-responders.

Disease Control Rate (DCR) per RECIST (v1.1) is defined as the percentage of patients with BOR of a documented complete response, partial response, and stable disease (CR + PR + SD), based on RECIST 1.1, by investigator assessment.

Duration of Response (DOR) per RECIST (v1.1) is defined as the time from the first documentation of a response (CR or PR) until time of first documentation of disease progression by RECIST (v1.1), or death by any cause.

1.2.1.2.2. Best Overall Responses, Objective Response Rate, Disease Control Rate and Duration of Response per iRECIST

Best Overall Response per iRECIST (iBOR) is the best response recorded from first dose until confirmed progression of disease (iCPD) or start of new anti-cancer therapy. In accordance with iRECIST, patients with stable disease (iSD) or better after an initial unconfirmed progression of disease (iUPD) are evaluated after iUPD for iCR (complete response)/iPR (partial response)/iSD (stable disease) in the determination of iBOR. Tumor scan assessment done after iCPD or after “new anti-cancer”

treatment will not be considered in the evaluation of iBOR. iBOR is derived from the sequence of objective response determined by the following order:

- iCR: One objective status of iCR documented before iCPD or start of new anti-cancer therapy
- iPR: One objective status of PR documented before iCPD or start of new anti-cancer therapy, but not qualifying as iCR
- iSD: At least 1 objective status of iSD or better documented within at least 1 nominal scan interval (6 weeks – 2 days window = 40 days) after first dose date or from previous adequate tumor assessment and before iCPD and the start of new anti-cancer therapy, but not qualifying as iCR or iPR
- iUPD (unconfirmed progression of disease): iUPD documented after first dose date and not qualifying as iCR, iPR, or iSD
- iCPD (confirmed progression of disease): iCPD documented and not qualifying as iCR, iPR, or iSD or iUPD
- NE: All other cases will be categorized as NE.

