	To evaluate the antitumor activity of DSP-7888 Dosing Emulsion administered with pembrolizumab in terms of the CA-125 response rate and time to progression with CA-125 criteria in PROC	
 1. CA-125 response rate is defined as proportion of patients who have achieved response using the Gynecologic Cancer InterGroup (GCIg) CA-125 response definition 2. Time to progression with CA-125 is defined as the time from the date of the first dose of study treatment to the earlier date of assessment of progression by GCIg CA-125 progression definition or death by any cause
	To characterize PD or potential predictive biomarkers and their relationship to clinical activity	
Biomarkers using peripheral blood samples and tumor tissue samples in patients receiving DSP-7888 Dosing Emulsion in combination with pembrolizumab may be evaluated for correlation with the following immunologic changes and/or clinical responses
 
 1. WT1-specific CTL induction activity in blood samples 2. WT1 expression level via CISH and PD-L1 expression status (CPS) via IHC in tumor tissue 3. CD8+ cell density in tumor tissues 4. TILs profiling in tumor tissues 5. Immune profiling in tumor tissues with tumor inflammation signature analysis 6. Mutation status and mutational burden analysis in tumor tissues 7. HLA typing

*Note: These samples must contain sufficient tumor tissue. Details of the biopsy time points are described in the SOA in Protocol Amendment 6 Table 9.

1.2.2.1. Primary Endpoint:

Primary Endpoint of phase 2 part is ORR per RECIST (v.1.1) based on investigator assessment (refer to Section 1.2.1.2.1 for the definition.)

1.2.2.2. Secondary Endpoints:

Secondary endpoints include DOR, DCR, PFS, 6 – month PFS rate per RECIST (v1.1) (refer to for Section 1.2.1.2.1 Section 1.2.1.2.3 for definitions.) ; iORR, iDCR , iDOR and iPFS per iRECIST based on investigator assessment (refer to Section 1.2.1.2.2 Section 1.2.1.2.4 for definition) ; and OS (refer to Section 1.2.1.2.5 for definition).

Safety assessment of frequency and intensity of AEs assessed according to CTCAE v4.03. also included a secondary endpoint.

1.2.2.3. Exploratory Endpoints:

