2.2. Statistical Decision Rules

For Phase 2 Cohort Only

There is no formal hypothesis testing for the Phase 2 cohort. A Bayesian decision-making framework will be employed to quantify whether proof of concept (POC) can be established based on the overall response rate (ORR) by Week 24 from the final analysis for the overall population and/or the CPS < 10 subpopulation. The POC is established at the final analysis if either or both of the following 2 conditions are met:

- In the overall population, 70% credible interval of ORR with 10% in the left tail and 20% in the right tail will be calculated: if lower bound $\geq 8\%$ and upper bound $\geq 21\%$ (where 8% is the reference value [Protocol Amend 6, Section 4.3.1; Matulonis, 2019] and 21% is the target value of ORR in the overall population), the study will achieve POC.
- In the CPS < 10 subpopulation, 50% credible interval of ORR with 20% in the left tail and 30% in the right tail will be calculated: if lower bound $\geq 5\%$ and upper bound $\geq 15\%$ (where 5% is the reference value [Protocol Amend 6, Section 4.3.1; Matulonis, 2019] and 15% is the target value of ORR in CPS < 10 subpopulation), the study will achieve POC.

The interim monitoring analysis for futility early efficacy assessment will be conducted using a Bayesian method and will start after the first 20 patients have response evaluation, withdraw, or die by Week 24.

- If the posterior probability of ORR $\geq 21\%$ in the overall population is $\leq 2.5\%$ AND the posterior probability of ORR $\geq 15\%$ in the CPS < 10 subpopulation is $\leq 2.5\%$, the study is futile and further enrollment will be stopped.
- If the posterior probability of ORR $\geq 21\%$ in overall population is $\geq 80\%$ AND the posterior probability of ORR $\geq 15\%$ in CPS < 10 subpopulation is $\geq 70\%$, then early success is met and further enrollment may be stopped.
- Otherwise, the enrollment will continue as is until 40 patients.

The above decision rules for interim analysis are non-binding.

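### The Phase 2 primary ORR is based on an Efficacy Set that keeps every responder but drops early-leaving non-responders, so any bias in ORR and in proof of concept is upward

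*Protocol*

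**What the plan says.** **Population for the primary analysis.** The Statistical Methods part of the protocol synopsis states that for Phase 2 "primary efficacy of ORR with RECIST v 1.1 will be analyzed using the Bayesian approach defined in the SAP, based on ES", and places the other efficacy analyses on the Full Analysis Set (FAS), which is all treated patients. Protocol 12.1.5.1 has the parallel sentence, "In Phase 2, primary efficacy of ORR will be analyzed using the Bayesian approach defined in the SAP", but names no set for it.

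**Who is in the ES.** Protocol 12.1.2.4 says that the ES "includes all patients from the FAS who have responded to treatment (CR/PR), assessed as progressed on treatment without regard to length of treatment". The third and last way in is at least 6 months on treatment, whatever the response.

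**How the SAP treats early leavers.** SAP 1.2.1.2.1 says "The patients will be considered as non-responders until proven otherwise". Its list of non-responders covers patients without a baseline or post-baseline tumor evaluation and patients who "Die, progress, or drop out for any reason prior to reaching a CR or PR". SAP 1.2.2.1 carries this into Phase 2: "Primary Endpoint of phase 2 part is ORR per RECIST (v.1.1) based on investigator assessment (refer to Section 1.2.1.2.1 for the definition".

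**Decision rules.** SAP 2.2 decides POC "based on the overall response rate (ORR) by Week 24 from the final analysis for the overall population and/or the CPS < 10 subpopulation". Neither 2.2 nor 5.3 says which analysis set supplies the denominator. SAP section 3 defines only the FAS and the Safety Set; the ES survives there as an abbreviation.

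**Precedence.** Protocol 12.1 lets the SAP modify the plan, but "any major modifications of the primary endpoint definition and/or its analysis will also be reflected in a protocol amendment".

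**The concern.** ES membership depends on the outcome. All responders enter. A non-responder enters only by progressing on treatment or by staying on treatment for 6 months. Patients who die, withdraw consent, stop for toxicity or have no post-baseline scan before then fall out of the denominator. So do patients whose progression is documented only after treatment has stopped. The SAP puts these same patients in the denominator as failures, for the same endpoint.

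The POC rule compares ORR with fixed values: 8% and 21% overall, 5% and 15% in the CPS < 10 subpopulation. There is no control arm in which a similar loss could offset the bias. Removing only non-responders therefore makes a false POC more likely, and the documents do not settle which denominator applies.

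**Working it through.** The documents give no prior, power, false-positive rate or responder cut-off for Phase 2, so there is no design figure to reproduce.

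**Inputs from the documents**
- About 40 Phase 2 patients (protocol 12.1.1.2).
- Overall POC: 10th posterior percentile at least 8% and 80th percentile at least 21%.
- CPS < 10 POC: 20th percentile at least 5% and 70th percentile at least 15%.
- Interim early success, after the first 20 patients: P(ORR ≥ 21%) at least 80% overall and P(ORR ≥ 15%) at least 70% in CPS < 10.
- Pembrolizumab-alone ORR of 8.0% overall, 17.1% for CPS ≥ 10 and about 5% for CPS < 10 (protocol 4.3.1).

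**Assumptions**
- Prior Beta(1,1) (uniform) or Beta(0.5,0.5) (Jeffreys).
- 0%, 5%, 10%, 15% or 25% of non-responders missing from the ES.
- 30 of 40 patients with CPS < 10, because the three ORRs imply a share of (17.1 − 8.0)/(17.1 − 5.0) = 75.2%.

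**Step 1: direction.** With x responders among n, the posterior is Beta(a + x, b + n − x). Removing k non-responders leaves x unchanged and lowers the second parameter to b + n − k − x. The observed rate becomes x/(n − k) ≥ x/n, and every posterior percentile and upper-tail probability rises. This needs no assumption about the prior or the loss. The ES wording does not require confirmed response, but an unconfirmed responder simply enters as a non-responder, so the direction is unchanged.

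**Step 2: how many exclusions change a decision**

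| Rule | Prior | All patients kept | After exclusions |
|---|---|---|---|
| Overall | Uniform | 5/40: 7.9% and 18.6%, fails | 5/35: 9.0% and 21.1%, passes |
| Overall | Jeffreys | 6/40: 9.0% and 20.4%, fails | 6/38: 9.5% and 21.5%, passes |
| CPS < 10 | Uniform | 3/30: 70th percentile 14.9%, fails | 3/29: 15.4%, passes |
| Interim P(ORR ≥ 21%) | Uniform | 5/20: 73.2%, below 80% | 5/18: 80.7%, meets 80% |
| Interim P(ORR ≥ 21%) | Jeffreys | 5/20: 68.5%, below 80% | 5/17: 80.8%, meets 80% |

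The interim rows apply only if the ES was used at the interim, and the CPS < 10 condition must also hold.

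**Step 3: probability of POC at the reference ORR.** Exact enumeration: X ~ Bin(n, p) responders, K ~ Bin(n − X, loss) non-responders excluded, rule applied to X out of n − K.

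| Rule and prior | 0% | 5% | 10% | 15% | 25% |
|---|---|---|---|---|---|
| Overall, n = 40, p = 8%, uniform | 9.7% | 10.0% | 12.8% | 17.1% | 26.0% |
| Overall, n = 40, p = 8%, Jeffreys | 3.8% | 6.8% | 9.5% | 12.6% | 19.9% |
| CPS < 10, n = 30, p = 5%, uniform | 6.1% | 15.6% | 18.2% | 19.9% | 29.1% |
| CPS < 10, n = 30, p = 5%, Jeffreys | 6.1% | 8.0% | 12.6% | 16.2% | 20.3% |

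In the overall population the mean ORR moves from 8.0% to 8.4%, 8.8%, 9.3% and 10.4% at the same losses.

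**Step 4: sensitivity to the CPS < 10 count.** With the uniform prior and n = 28, the probability is 16.3% at 0% and 5% loss, 17.3% at 10% and 20.9% at 15%. With n = 32 it is 7.4% at no loss and 19.3% at 15%. The jump at n = 30 comes partly from the discreteness of the cut-off.

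**The case against.** **The current SAP no longer uses the ES, and efficacy is dropped from the final report.** True. SAP v3.0 records that Phase 2 stopped on interim monitoring, and SAP 5.5 only lists responses. This limits the consequence. It does not resolve the text, because the synopsis still names the ES and the SAP names nothing in its place for the POC rule.

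**The interim count includes patients who withdraw or die, which suits an all-treated denominator.** This is a fair reading and makes ES use at the interim less likely. It remains an inference, since neither document says so. Upward bias also makes futility harder to declare, so it could not have caused a wrong futility stop. The documents do not say which interim rule was met.

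**SAP 5.3 continues enrolment to 40 evaluable patients, whereas SAP 2.2 says 40 patients.** If evaluable meant ES members, the ES would not shrink below 40. At 5%, 10% and 15% loss the CPS < 10 probability (30 evaluable) would then go from 6.1% to 7.0%, 8.1% and 9.5% under both priors. The overall Jeffreys value would go from 3.8% to 4.7%, 5.8% and 7.3%, and the overall uniform value from 9.7% to 11.5%, 13.6% and 16.2%. The bias is then smaller in most cases but still upward, and the two wordings are a further sign that the denominator is unsettled.

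**The SAP text classifies responses and does not define a population.** Correct. The conflict is one of effect: patients whom the SAP makes failures are missing from the ES denominator.

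**Conclusion.** The concern holds. The synopsis bases the primary Phase 2 ORR on a set selected by outcome, the SAP counts the excluded patients as non-responders, and no other section reconciles the two. The upward direction is certain whenever anyone is excluded; the bias is zero if nobody is.

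The size is a range resting on assumed priors and losses. At a true ORR of 8% in 40 treated patients, the false-POC probability in the overall population rises by between 0.3 percentage points (5% loss, uniform: 10.0 − 9.7) and 16.3 points (25% loss, uniform: 26.0 − 9.7). The CPS < 10 figures also depend on the assumed subgroup size, so the n = 30 result should not be read as an estimate.

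The remaining exposure is the interim decision already taken, any ORR quoted from the listings, and any later use of the POC rules that SAP 2.2 and 5.3 still carry. It should be corrected, but it does not undermine the safety report now planned.

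**What to change.** - **Protocol synopsis:** base the Phase 2 primary ORR on the FAS instead of the ES.
- **SAP 2.2 and 5.3:** state that ORR, the interim posterior probabilities and the POC credible intervals use all FAS patients, and all FAS patients with CPS < 10 for the subpopulation, with the non-responder rule of SAP 1.2.1.2.1. In the same edit, reconcile 40 patients with 40 evaluable patients.
- **ES:** keep any ES result only as a labelled sensitivity analysis.
- **Synoptic study report:** state which set and which denominators the interim decision used, and list ORR on the FAS.

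The cost is one line in a protocol amendment, one sentence in each SAP section and one in the report. No new data are needed. An amendment also requires ethics re-approval (protocol 15.1), which is a real burden for a part that has stopped. If that is judged disproportionate, the report sentence is the minimum, and the SAP sentences should still be made. ORR may look slightly less favourable. With all 40 patients kept, the probability of overall POC at a true ORR of 21% is 87.3% (uniform) or 76.4% (Jeffreys).

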### **12.1.3. Handling of Missing Data**

No missing data will be imputed, except missing start/end date of concomitant medication. The rule of imputation will be defined in the SAP.

#### **12.1.4. Demographic and Baseline Characteristics**

Baseline is defined as the last non-missing measurement taken before receiving the first dose of study drug. All applicable demographic and baseline characteristics will be summarized with descriptive statistics.

#### **12.1.5. Data Analyses**

##### **12.1.5.1. Efficacy Analysis**

Kaplan-Meier methods will be used to summarize time-to-event endpoints (OS, PFS, and DOR). Primary efficacy of ORR will be analyzed using the Bayesian approach defined in the SAP; other efficacy analyses will be performed on the FAS.

Patient responses will be assessed based on RECIST v1.1 and iRECIST. Data listings and summaries may include tumor markers, additional imaging, or other response data. Potential relationships between PD and other response data may be evaluated. In Phase 2, primary efficacy of ORR will be analyzed using the Bayesian approach defined in the SAP; other efficacy analyses will be performed on the FAS.

Progression-free survival ratio (PFSr) will be summarized for both the Phase 1b enrichment cohort and for Phase 2.

##### **12.1.5.2. Safety Analysis**

Adverse events will be assessed according to CTCAE v4.0,3 when appropriate, and will be evaluated by grade and System Organ Class (SOC). Adverse event listings and tabulated summaries of categorized AEs will be generated by dose level and patients overall, for each study arm, and study phase. Additionally, the number of patients enrolled, number evaluable for dose search, and number with DLTs will be described for each dose level, by patients overall, and for each study arm in Phase 1b, the dose-search part of the study. Vital signs, laboratory data, and ECG data stratified by dose level and overall for each study arm and phase will be summarized for changes over time at each post-baseline visit, together with the change from baseline.

